2.10 Patient-reported outcomes

All PRO endpoints will be summarized using SAF. The data will be analyzed.

Refer to the UAS7, HSS7, ISS7 and DLQI analyses described in [Section 2.6](#) in this document.

2.10.1 Dermatology Life Quality Index (DLQI)

The Dermatology Life Quality Index (DLQI) is a 10-item dermatology-specific health-related quality of life measure presented to each subject, from baseline (Visit 110, Day 1) up to the study end. The DLQI total score will be calculated by summing the score of each question resulting in a maximum of 30 and a minimum of 0.

For DLQI, the domain scores are calculated for:

[figure not shown]
Symptoms and Feelings (0-6), Daily Activities (0-6), Leisure (0-6), Work and School (0-3), Personal Relationships (0-6) and Treatment (0-3) (see detail definitions in [Table 2-2 DLQI domains](#)).

Table 2-2 DLQI domains

[figure not shown]
Domain	Relevant Question	Maximum score
Symptoms and feelings	Questions 1 and 2	6
Daily activities	Questions 3 and 4	6
Leisure	Questions 5 and 6	6
Work and school	Question 7	3
Personal relationships	Questions 8 and 9	6
Treatment	Question 10	3

Missing data handling for DLQI

For the DLQI subscale and total score derivation, if there is only one missing score per visit, then it will be imputed to 0 and then the subscale including this item and the total score will be calculated accordingly. If there are two or more missing scores per visit, then the score will be missing.

A horizontal bar chart consisting of 20 black bars of varying lengths, arranged in two groups of 10. The bars are set against a white background with thin white gaps between them. The top group of bars is generally longer than the bottom group.

The image shows a series of horizontal black bars of varying lengths, representing redacted text lines. The bars are positioned in a grid-like pattern, with some lines having small gaps between them. The bars are black and have a consistent thickness. The background is white, and the bars are evenly spaced vertically.

2.13 Interim analysis

Not Applicable.

3 Sample size calculation

3.1 Primary endpoint(s)

No formal statistical power calculations to determine sample size were performed for this study. The sample size is determined based on the regulatory requirement by Pharmaceuticals and Medical Devices Agency (PMDA) to fulfill the long term safety data for Japanese patients. Considering 10% drop out rate based in the QGE031C2201 study, the planned sample size (N=65) in this study will have 58 patients with 1 year exposure, and it is expected to have 100 Japanese patients exposed to ligelizumab with 1 year in the total ligelizumab CSU program, together with QGE031C2201/E1 and QGE031C2303 studies. With the total sample size (N=100) exposed to ligelizumab in Japanese patients, one can expect to see at least one patient with a specific AE with 95% probability, assuming the occurrence rate of an AE is 3%, aligned with ICH E1 guideline. Safety data from the study will also be evaluated together with Japanese patients from other ligelizumab studies in the submission dossier.

3.2 Secondary endpoints(s)

The expected half-width of 95% confidence interval for the change from baseline in UAS7 would be 3.3, assuming 58 patients (10% missing) are available of post-baseline UAS7 data and SD=13. If the mean change from baseline in UAS7 for ligelizumab group is -22.0 (based on C2201 study at Week 12), 95% confidence interval of the mean change from baseline in UAS7 will be (-25.3, -18.7).

4 Change to protocol specified analyses

No change from protocol specified analysis is made.

5 Appendix

5.1 Derivation rules for end of treatment date

The end of treatment date up to Week 52 treatment period is defined as below.

1. If patients complete treatment period, the end date is the first non-missing date of the following dates: Week 52 dosing date, Week 52 visit date, PD date of missing visit at Week 52, first dosing date + 52 weeks.
2. If patients early discontinue treatment before Week 52, the end date is the first non-missing date of the following dates: last dosing date + 4 weeks, last visit date, PD date of missing visit at Week 52, first dosing date + 52 weeks.

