Rescreening may be allowed for subjects who failed initial screening. Only 1 rescreening will be allowed (see [Section 5.1](#) and [Section 5.2](#)). If a subject is rescreened for the study, the subject must sign a new informed consent and will be issued a new subject number. Informed consent for a rescreened subject must be obtained prior to performing any study-related assessments or collecting any data for the Screening visit.

Treatment period

On Day 1, eligible subjects will enter an open-label treatment period to receive ligelizumab 120 mg sc q4w. The first dose of study drug will be administered on Day 1 (Visit 110). The last dose of ligelizumab 120 mg will be administered on Day 337 (Week 48, Visit 230) study visit.

Approximately 65 subjects will be allocated to the ligelizumab 120 mg q4w arm. Subjects are expected to attend all site visits based on the assessment schedule ([Table 8-1](#)).

Post-treatment follow-up period

The post-treatment follow-up period is 12 weeks with the last follow-up visit (Visit 1999) corresponding to 16 weeks after the last treatment dose. No investigational treatment will be given during the post-treatment follow-up period. Subjects will be allowed to take their rescue medication on an as needed basis, assessed on a daily basis by the subjects. Subjects will be required to visit the study center every 4 weeks during the post-treatment follow-up period.

Patients will be eligible for post-trial access after completion of the study.

4 Rationale

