6.1.3 Treatment arms/group

All eligible subjects will be assigned at Visit 110 to ligelizumab group. Each subject will receive 1 injection of 1.0 mL ligelizumab every 4 weeks.

During the treatment period, study drug will be administered for 13 visits as per [Table 8-1](#).

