6.2.2 Prohibited medication

Use of the class of treatments displayed in [Table 6-2](#) is NOT allowed after start of screening. The minimum required period without prohibited treatment before Visit 1 is also listed in [Table 6-2](#). Each concomitant medication must be individually assessed against all exclusion criteria and the table below to see if it is allowed. If in doubt, the investigator should contact Novartis medical monitor or delegate before entering a subject to treatment period or allowing a new medication to be started.

Table 6-2 Prohibited medication

Medication	Minimum required period without medications
Omalizumab	4 months prior to Visit 1
Ligelizumab	No prior use allowed
Routine (more than 3 doses over a 5 day period) oral corticosteroids*	30 days prior to Visit 1
IV/IM/IA corticosteroids	30 days prior to Visit 1
Beta-blocker therapy	7 days prior to Visit 1
Leukotriene antagonists	Stop at Visit 1
H2-antihistamines	Stop at Visit 1
First generation H1-antihistamines	Stop at Visit 1
Hydroxychloroquine or chloroquine	30 days prior to Visit 1
Other immunosuppressive medication with or without known effect on CSU including but not limited to Methotrexate, cyclosporine A, cyclophosphamide, tacrolimus and mycophenolate mofetil	30 days prior to Visit 1
Intravenous immunoglobulin G	30 days prior to Visit 1

Medication	Minimum required period without medications
Plasmapheresis	30 days prior to Visit 1
Regular (daily or every other day) doxepin (oral)	14 days prior to Visit 1
Vaccination with inactivated viruses	48 hours prior to each dosing visit (i.e. Visit 110 to Visit 230)
Live attenuated vaccine	30 days prior to Visit 1
[REDACTED]	[REDACTED]

* Allowed only as rescue therapy only after Week12, on an as-needed basis for unbearable symptoms as per [Section 6.2.3](#). Other preparations of CS with limited systemic exposure for non-CSU indications can be used (e.g. Intra nasal or topical CS) as needed basis.

If the prohibited treatment was used during the study for any indication, the subject must discontinue use of the prohibited treatment if he/she wishes to continue in the study. If the subject received a live virus vaccination during the study, the subject must discontinue study treatment.

If a subject takes concomitant omalizumab (outside of study assigned tr [REDACTED] in the follow-up phase, the subject must discontinue from the study, in which case [REDACTED] ADA samples should not be collected at the End of Study (EoS) visit.

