6.6 Additional treatment guidance

6.6.1 Treatment compliance

Subjects will receive 1 subcutaneous injection every 4 weeks at 13 visits during the treatment period. Compliance is assured as study drug must/ will be administered by investigator and/or study personnel via subcutaneous injection at the site. Administration of study drug must be recorded in the source documents and the corresponding eCRF for each administration.

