Subjects must be seen for all visits on the designated day, or as close to it as possible. The subject should be instructed to contact the investigator if he/she is unable for any reason to attend the visit as planned and the visit should be rescheduled as close as possible to the original date. Missed or rescheduled visits should not lead to automatic treatment or study discontinuation.

All subjects who complete the treatment period will be expected to attend all follow-up visits (Visit 310 to 1999).

Subjects who discontinue treatment early will be expected to perform the Week 52 assessment (last visit in the treatment period) 4 weeks after they receive their last dose. At the final visit, all dispensed investigational product should be reconciled and the adverse event and concomitant medications reconciled on the eCRF.

Table 8-1 Assessment Schedule

Period	Screening	Treatment															Follow-up			Unplanned
Visit Name	1	110	120	130	140	150	160	170	180	190	200	210	220	230	240/EoT/TD ¹	310	320	1999/EoS/PSD ²	UPV ³	
Days	-28 to -14	1	29	57	85	113	141	169	197	225	253	281	309	337	365	393	421	449	-	
Weeks	-4 to -2	0	4	8	12	16	20	24	28	32	36	40	44	48	52	56	60	64	-	
Informed consent	X ⁴																			
Inclusion / Exclusion criteria	X	X																		
Demography	X																			
Relevant medical history (including CSU history)	X																			
Evidence of urticaria	X																			
Prior urticaria treatment	X																			
Family malignancy history (CRF to be completed if subject develops malignancy during the study)	X																			
Prior and Concomitant medication usage	X	X	X	X	X	X	X	X	X	X	X	X	X	X	X	X	X	X	X	
Surgery and procedures	X	X	X	X	X	X	X	X	X	X	X	X	X	X	X	X	X	X	X	
Re-screening (re-screening eCRF should be recorded if the subject is re-screened)	X																			
Dispense H1-AH rescue medication	S	S	S	S	S	S	S	S	S	S	S	S	S	S	S	S	S			
Dispense oral corticosteroid rescue medication ¹⁴					S	S	S	S	S	S	S	S	S	S	S	S	S			
Study drug administration		X	X	X	X	X	X	X	X	X	X	X	X	X	X					

Period	Screening	Treatment														Follow-up			Unplanned
		110	120	130	140	150	160	170	180	190	200	210	220	230	240/EoT/TD ¹	310	320	1999/EoS/PSD ²	
Visit Name	1																		UPV ³
Days	-28 to -14	1	29	57	85	113	141	169	197	225	253	281	309	337	365	393	421	449	-
Weeks	-4 to -2	0	4	8	12	16	20	24	28	32	36	40	44	48	52	56	60	64	-

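### The protocol text ends dosing at Week 48 after 13 doses, but Table 8-1 as read shows a 14th dosing mark at Week 52 and SAP 5.1 names a Week 52 dose date

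*SAP*

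**What the plan says.** Four places in the protocol text describe one schedule:

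- Section 3, Treatment period: "The last dose of ligelizumab 120 mg will be administered on Day 337 (Week 48, Visit 230) study visit".
- Section 6.1.3: "During the treatment period, study drug will be administered for 13 visits as per" Table 8-1.
- Section 6.6.1: "Subjects will receive 1 subcutaneous injection every 4 weeks at 13 visits during the treatment period".
- Section 6.2.2, Table 6-2, in the row on inactivated vaccines: "48 hours prior to each dosing visit (i.e. Visit 110 to Visit 230").

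Protocol section 3 and SAP 1.1 both place the final visit (Visit 1999) 16 weeks after the last dose.

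Two places do not fit this. The Table 8-1 row headed "Study drug administration" has 14 marks, from Visit 110 to Visit 240/EoT/TD (Week 52, Day 365). For subjects who complete treatment, SAP 5.1 gives a "Week 52 dosing date" first place: it says that "the end date is the first non-missing date of the following dates: Week 52 dosing date, Week 52 visit date", followed by two further fallbacks. SAP section 4 reports no change from the protocol's analyses.

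**The concern.** Section 6.1.3 rests its count of 13 on a table that, as read, shows 14. Section 3 ties attendance to the same table, so a dosing mark at Visit 240 could be acted on. That mark also sits oddly with the visit's other role: sections 8 and 9.1.1 have early discontinuers attend the Week 52 assessment four weeks after their last dose.

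Several analysis quantities are anchored on the last dose:

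- the exposure duration (SAP 2.4.1);
- the 16-week window for treatment-emergent events, which defines the primary variable (SAP 2.5.1 and 2.5.2);
- the four-week window for treatment-phase events (Protocol 12.5.2).

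The SAP's time-to-loss-of-response analysis also starts at Week 52, which would be a dosing day under one schedule and four weeks after dosing under the other.

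**Working it through.** **Inputs.** First dose Day 1; interval 28 days; last dose Day 337 (Protocol section 3) or Day 365 (last mark in the Table 8-1 row); Visit 1999 on Day 449 (Table 8-1). Exposure is last dose minus first dose plus 28 days (SAP 2.4.1). The treatment-emergent window is 16 weeks, or 112 days, after the last dose (SAP 2.5.1). Adverse-event monitoring runs at least 30 days past the last dose or the end-of-study visit, whichever is longer (Protocol 10.1.1).

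**Step 1: reproduce the protocol text.** Number of doses = (337 − 1)/28 + 1 = 13. Last dose to final visit = 449 − 337 = 112 days = 16 weeks. Both agree with the text, so the prose is internally consistent.

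**Step 2: read the table row.** The study-drug row splits into as many cells as the Visit Name and Days rows (21 each, including the label). Its 14 marks fall under Visits 110 to 240/EoT/TD. Two neighbouring rows serve as a check. H1-antihistamine dispensing has 17 marks (Visits 1 to 320). Oral corticosteroid dispensing has 13 marks (Visits 140 to 320), starting at Week 12 in line with section 6.2.3. Both line up with the header.

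**Step 3: compare the two schedules.**

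| Quantity | Last dose Day 337 | Last dose Day 365 |
|---|---|---|
| Doses | (337 − 1)/28 + 1 = 13 | (365 − 1)/28 + 1 = 14 |
| SAP exposure | 336 + 28 = 364 days (52 weeks) | 364 + 28 = 392 days (56 weeks) |
| Last dose to Visit 1999 | 449 − 337 = 112 days (16 weeks) | 449 − 365 = 84 days (12 weeks) |
| End of 16-week event window | 337 + 112 = Day 449 (Week 64) | 365 + 112 = Day 477 (Week 68) |
| End of 4-week treatment-phase window | 337 + 28 = Day 365 | 365 + 28 = Day 393 (Week 56) |

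**Step 4: is the longer window still observed?** 477 − 449 = 28 days past the last scheduled visit, and past the 64-week period in which SAP 2.5.1 counts the primary variable. Monitoring after Visit 1999 runs to at least 449 + 30 = Day 479, which is later than Day 477.

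**Step 5: does the SAP 5.1 wording move any date?** The rule takes the first non-missing date. Without a Week 52 dose it passes to the Week 52 visit date, planned for Day 365. With one, the dosing date is also planned for Day 365. The planned end-of-treatment date is the same either way.

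**The case against.** The strongest reply is that this is one stray mark. All four prose statements agree, the visit is labelled end of treatment, and section 6.1.3 shows that its authors took the table to hold 13 dosing visits. The table was also read by machine, and its continuation is visibly damaged. The hematology row keeps only 7 marks. The last two antibody marks sit one column to the left of the sampling log in Appendix 5. The eDiary-collection mark falls under Visit 320. The footnote attached to the Visit 240 column is not in the available text and might address the point.

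Much of this stands. The fourteenth mark must be confirmed on the original page before anything is built on it. But a column shift would move a mark, not add one, and the block holding the dosing row aligns where it can be checked. SAP 5.1 is prose and does not depend on the table.

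Three stronger readings are tempting, and the documents support none of them:

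- **That the SAP schedules a Week 52 dose.** It lists a possible date in a fallback chain. Exposure is computed separately, from actual dosing dates.
- **That the event window would outrun data collection.** Step 4 shows that it stays within the monitoring period. A narrower point remains: section 10.1.3 sends serious events after the last visit to the safety database only, not to the eCRF.
- **That exposure-adjusted rates would count time beyond the study.** SAP 2.7.1.1 takes the shortest of three times, one of which is the end of the analysis period at Week 64.

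**Conclusion.** The contradiction is credible and should be resolved: 13 dosing visits ending at Week 48 in the protocol text, against 14 marks ending at Week 52 in the table that the text cites, with independent wording in SAP 5.1 that allows for a dose at Week 52. This rests on the fourteenth mark being present in the original table.

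The consequences are conditional. The figures of 14 doses, 392 days and 84 days apply only to a subject who is actually dosed at Week 52. That a site would do so from the table is an assumption. A reader might infer that the trial has only 12 weeks of follow-up after the last dose; under the protocol text it has 16. If no Week 52 dose is given, no derived date changes.

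**What to change.** Confirm the study-drug row, and the footnote to the Visit 240 column, on the original page of Table 8-1. Then reconcile Table 8-1, Table 6-2, Protocol sections 3, 6.1.3 and 6.6.1, and SAP 5.1, so that all name the same last dosing visit. Check that the 16-week follow-up, the treatment-emergent window, the four-week treatment-phase window and the end-of-treatment rule agree with it. Which schedule applies is for the sponsor to state. The cost is a correction to a table and some wording; no new data are needed.

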5.2 Imputation rules

5.2.1 Study drug

No imputation of missing/partial start or study end date drug. If missing, the time of study end date will be imputed to 00:00:00.

5.2.2 AE date imputation

Rules for imputing the AE end date:

- If the AE end date month is missing, then the imputed end date should be set to the earliest of the study end date, 31DECYYYY or date of death.
- If the AE end date day is missing, then the imputed end date should be set to the earliest of the study end date, last day of the month or date of death.
- If AE year is missing or AE is ongoing, then the end date will not be imputed.

Rules for imputing the AE start date:

- If imputing end dates, then this should be done prior to calculating imputed start dates.

The following table explains the notation used in the logic matrix. Please note that **missing start dates** will not be imputed.

	Day	Month	Year
Partial Adverse Event Start Date	Not used	MON	YYYY
Treatment Start Date	Not used	TRTM	TRTY

The following matrix explains the logic behind the imputation.

	MON MISSING	MON < TRTM	MON = TRTM	MON > TRTM
YYYY MISSING	(1) No convention			
YYYY < TRTY	(a) Before Treatment Start	(b) Before Treatment Start	(b) Before Treatment Start	(b) Before Treatment Start
YYYY = TRTY	(a) Uncertain	(b) Before Treatment Start	(c) Uncertain	(c) After Treatment Start
YYYY > TRTY	(a) After Treatment Start	(b) After Treatment Start	(b) After Treatment Start	(b) After Treatment Start

Before imputing AE start date, find the AE start reference date.

1. If the (imputed) AE end date is complete and the (imputed) AE end date < treatment start date, then AE start reference date = min(informed consent date, earliest visit date).
2. Otherwise, AE start reference date = treatment start date.

Impute AE start date:

1. If the AE start date year value is missing, then the date uncertainty is too high to impute a rational date. Therefore, if the AE year value is missing, then the imputed AE start date is set to NULL.
2. If the AE start date year value is less than the treatment start date year value, then the AE started before treatment. Therefore:
 - a. If AE month is missing, then the imputed AE start date is set to the mid-year point (01JulYYYY).
 - b. Otherwise, if AE month is not missing, then the imputed AE start date is set to the mid-month point (15MONYYYY).
3. If the AE start date year value is greater than the treatment start date year value, then the AE started after treatment. Therefore:
 - a. If the AE month is missing, then the imputed AE start date is set to the year start point (01JanYYYY).
 - b. Otherwise, if the AE month is not missing, then the imputed AE start date is set to the later of month start point (01MONYYYY) or AE start reference date + 1 day.
4. If the AE start date year value is equal to the treatment start date year value:
 - a. If the AE month is missing, then the imputed AE start date is set to the AE reference start date + 1 day.
 - b. If the AE month is less than the treatment start month, then the imputed AE start date is set to the mid-month point (15MONYYYY).
 - c. Otherwise, if the AE month is equal to the treatment start date month or greater than the treatment start date month, then the imputed AE start date is set to the later of (month start point (01MONYYYY), AE start reference date + 1 day).

If complete (imputed) AE end date is available and the imputed AE start date is greater than the (imputed) AE end date, then imputed AE start date should be set to the (imputed) AE end date.

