2.7.1.2 Adverse events of special interest / grouping of AEs

Refer to the AEs analyses described in [Section 2.5](#) in this document.

Adverse events of special interest

The following adverse events of special interest (AESI) will be summarized separately by each category and SOC/PT.

Details will be provided in the separate document (eCRS). The search criteria in the latest eCRS corresponding the MedDRA version at the database lock will be used and reported in the CSR.

- Hypersensitivity reactions (including anaphylaxis)
- Cardiovascular and Cerebrovascular (CCV) events
- Neoplastic conditions
- Injection site reactions
- Serum Sickness
- Eosinophilic Conditions / Churg-Strauss Syndrome

- Parasitic (Helminthic) infections
- Thrombocytopenia

Injection site reactions

For injection site reactions (ISR), besides the overall summary table for AESI, ISR will be summarized by events and subject separately in each treatment group for the following categorical variables.

The ISR selected by eCRS as ISR will be mapped to the exposure dosing window. The PTs (possible more than 1 records) happened during the same dosing window (on or after the drug injection administration date and before the next injection administration), they will be considered as one ISR event. If there is any missing dose injection occurred, any selected event will be all considered related to the last drug administration happened. For example, if a dose administration scheduled dose at Week 4 happened, and the next dose administration happened at Week 12 with Week 8 dose administration missing, all injection site reaction happened on or after Week 4 drug administration date before Week 12 drug administration date will be considered related to Week 4 drug administration.

If there were multiple PTs occurred during one dosing window, the worst case will be used for the summary and analysis of ISR. If there is any PT record detailed information (e.g. severity, resolution time, action or outcome etc..) missing or unknown, this PT record will not be included for the particular category summary of ISR. If all PT records for one ISR are with unknown/missing information for the summary category, the ISR will be summarized in the unknown category in the table.

- Recurrence of ISR (single ISR, 2-3 ISRs, > 3 ISRs)
- Severity of ISR (best to worst cases: mild, moderate, severe)
- Timing of ISR (during first administration, Week 4-Week 8, Week 8-Week 24, After Week 24)

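### If imputed start dates feed the injection-site-reaction mapping, a reaction to injections 2-13 with a missing start day is usually assigned to the previous injection

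*SAP*

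**What the plan says.** SAP 5.2.2 covers partial AE start dates. Where the month is known, the day is missing and the year is after the treatment-start year (rule 3b), "the imputed AE start date is set to the later of month start point (01MONYYYY) or AE start reference date + 1 day". Where the year is the treatment-start year and the month is the treatment-start month or later (rule 4c), the date is "set to the later of (month start point (01MONYYYY), AE start reference date + 1 day". For any event not known to have ended before treatment, "Otherwise, AE start reference date = treatment start date". If the imputed start falls after the end date, "then imputed AE start date should be set to the (imputed) AE end date". An end date without a day has its own rule: "the imputed end date should be set to the earliest of the study end date, last day of the month or date of death".

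SAP 2.7.1.2 then uses dates to attribute reactions: "The ISR selected by eCRS as ISR will be mapped to the exposure dosing window". A window covers events "on or after the drug injection administration date and before the next injection administration", and all ISR terms within one window count as one event. The resulting events are tabulated by recurrence, timing, time to resolution and other attributes, with a Kaplan-Meier curve for time to first ISR. A record lacking a given detail, resolution time being one named example, is left out of that category's summary.

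Neither section says whether imputed dates feed the window mapping or the resolution-time bands.

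**The concern.** The two rules work against each other. Attribution depends on which injection most recently preceded the reaction. The imputation rule knows only the first injection, and from the second injection on it places the start at the beginning of the month. With 28-day dosing, the 1st of the month nearly always precedes that month's injection, so the reaction is dated before the injection it followed.

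ISRs are an adverse event of special interest, and Protocol 4.5 reports a possible dose-related trend for them. With about 65 subjects, a few misplaced records can visibly change small category counts. SAP 2.7.1.2 takes care over attribution after a missed dose, but has no matching provision for partial dates.

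**Working it through.** The plan states no misallocation rate or duration error, so it has no figure to reproduce. The dosing calendar does check: 1 + 12 × 28 = Day 337, the last-dose day in Protocol section 3.

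**Inputs from the documents**
- 13 injections, 28 days apart (Protocol 6.6.1).
- Imputed start = max(1st of month, first injection + 1 day), capped at the AE end date (SAP 5.2.2).
- Window = from injection k up to, but not including, injection k+1 (SAP 2.7.1.2).
- Duration = end − start + 1 (SAP 2.1.1).

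**Assumptions not in the documents**
- Onset L = 0, 1 or 2 days after injection (7 as an extreme).
- True duration 1-3 days.
- First-dose dates spread evenly over the calendar.
- Complete end date unless stated otherwise.

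**Example.** Injections on 6 May and 3 June 2020; reaction on 3 June, recorded as June 2020. The imputed start is 1 June. Since 6 May ≤ 1 June < 3 June, it maps to the May injection.

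**Injections 2-13.** Let D be the day of the month of onset. The imputed 1st falls in the correct window only if D ≤ L + 1. That is 12 × (L + 1) dates in a 365-day year, so the share in the wrong window is 1 − 12(L + 1)/365:

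| Onset lag L | Wrong window |
|---|---|
| 0 days | 1 − 12/365 = 96.7% |
| 1 day | 1 − 24/365 = 93.4% |
| 2 days | 1 − 36/365 = 90.1% |
| 7 days | 1 − 96/365 = 73.7% |

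The mean shift is the average day of the month minus 1: (7 × 496 + 4 × 465 + 406)/365 − 1 = 5,738/365 − 1 = 14.7 days. The shift is at least 3 days when D ≥ 4, which is 1 − 36/365 = 90.1% of dates. A true one-day reaction would then last more than 3 days on paper.

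Enumerating 730 consecutive first-dose dates with the floor and cap applied gives the same percentages and mean, with a median shift of 15 days. Moving visits by up to ±3 days changes the pooled rates by less than 1 point.

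**Injection 1.** The floor keeps the start with the first injection: 0% misallocated, and a duration error of −1 to +1 day at lags of 0-2 days.

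**All 13 injections.** With equal frequency per dose, 12/13 × 96.7% = 89.3% at zero lag (86.2% and 83.2% at lags of 1 and 2 days). If 25%, 50% or 75% of ISRs follow the first dose, the zero-lag figure is 72.5%, 48.4% or 24.2%.

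**Timing bands.** Assign bands by mapped dose, with a shared boundary week counted in the later band. Then only the doses at Weeks 4, 8 and 24 change band when moved back one dose: 3/12 × 96.7% = 24.2%. The few records moved two doses back bring this to about 25%.

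**End day also missing.** The month-end rule adds to the error, and apparent duration grows by about 29.5 days for injections 2-13.

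**The case against.** A reader might infer that every ISR with a missing day is misplaced. That does not follow: the first injection is a floor in both rules, so first-dose reactions are safe, and the overall share depends on how many ISRs follow the first dose.

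A reader might also infer that reported resolution times will be about two weeks too long. The documents do not establish this. The bands are in hours, SAP 5.2.2 imputes whole dates, and SAP 2.7.1.2 leaves out records whose resolution time is unknown. A record with no start day can reasonably be read as one of those.

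Nor do recurrence counts have to fall. Two ISRs merge only if the earlier window already holds one. If one term from a window is fully dated and its companion lacks a day, the companion moves back and one ISR becomes two.

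There is also a fair case that little is at stake. Injections are given on site with 2 h or 30 min of observation (Protocol 6.7.2), AEs are sought at each visit (10.1.1) and missing values are queried (11.2). The ISR summaries are descriptive. For these records the imputed date stays within treatment, so treatment-emergent status, and with it the primary variable, is unaffected.

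All of this stands and limits the point. It does not remove the conflict for injections 2-13, or the silence on whether imputed dates are used.

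**Conclusion.** The point holds for injections 2-13, on condition that imputed dates enter the ISR mapping. The SAP states no ISR exception to its general AE rule. In that case a missing start day sends the reaction to an earlier injection in about 90-97% of cases at onset lags of 0-2 days, and still in 73.7% at 7 days. Timing and time to first ISR can shift only earlier, although the coarse timing bands change for roughly a quarter of such records. The effect on recurrence has no fixed direction, and the effect on time to resolution is conditional. The documents give no frequency of partial dates. This is a minor clarification, best settled before programming.

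**What to change.** Add to SAP 5.2.2: for AEs selected by the eCRS as ISR, with known month and missing start day, impute the start as the latest injection date in that month that is not after the AE end date; if there is none, apply the current rule. Add to SAP 2.7.1.2 that imputed starts are used for window mapping, and that time to resolution is treated as unknown when the start or end day is missing.

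With a complete end date, this brings misallocation for injections 2-13 to 0%. Using the first injection in the month instead would leave 8.1% at zero lag, because 28-day dosing puts two injections in some months.

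The cost is a few sentences and a small programming step using dosing dates already recorded. The rule assumes onset on an injection day. If the end day is also missing, about 7-13% of ISRs after injections 2-13 remain misallocated at lags of 0-2 days, and more at longer lags. In that situation some first-dose ISRs that now map correctly would move to the second injection (8.1%, 11.2% and 14.5% at lags of 0, 1 and 2 days).
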